11.0 Privacy/Confidentiality Issues

All efforts, within reason, will be made to keep protected health information (PHI) private. Using or sharing ("disclosure") such data will follow federal privacy rules.

As per standard practice at VUMC, we may share the results of the study and/or non-study linked lab tests, as well as parts of your medical record, with the Federal Government Office for Human Research Protections, the Vanderbilt University Institutional Review Board, The Food and Drug Administration, other government agencies throughout the world and insurance companies for billing purposes.

Data will be kept in for at least six years after the study is finished. There is no current intent to place data in the medical record. If subjects specifically request, we will store data indefinitely.

Novel Mechanisms and Predictors of VEGF Receptor Inhibitor- or Immune Checkpoint Inhibitor-Associated Hypertension and Cardiovascular Disease

NCT03709771

Date: October 30, 2018

Sample Size and Power Calculation:

Hypertension: In studies of TKI use, increases in blood pressure begin within days and reach steady state over weeks. Pazopanib has been shown to increase mean arterial blood pressure by 15 mm Hg in this time frame^{75,76}. Based on the previous studies, we assume it is reasonable to expect the mean changes of BP for placebo group is 15 mm Hg, the mean changes of BP for bosentan group is 7 mm Hg, the mean changes of BP for the ambrisentan group is 0 mm Hg, all with a standard deviation of 10 mm Hg. We first conducted power analysis with ANOVA framework. We planned to recruit 45 patients per group. In power calculation, to account for potential loss-to-follow issue that happens in almost every longitudinal studies, we considered 40 patients per group. With 40 subjects per group, we will have 100% power to detect whether there is any significant differences among three study arms. When comparing ambrisentan group to the placebo, with 40 subjects per group, we will have 100% power to detect whether there is significant difference between two groups. To be conservative, we set the mean changes of BP for placebo group to 12 mm Hg, the mean changes of BP for bosentan group to 6mm Hg. The analysis showed we still have 99.8% power to detect whether there is significant difference between groups.

We also evaluated the required minimum detectable effect size with 40 subjects per group to achieve 80% power. As can be seen from Figure 8, the minimum detectable effect size (f) required is about 0.29 (i.e., 7.7% of the total variance accounted for by groups). Although this is considered a medium effect size (f=0.25, Cohen, 1988), it is much smaller than the effect size we expected (f=0.61).

When comparing bosentan group to the placebo, with 40 subjects per group, we will have 86.8% power to detect whether there is significant difference between two groups. Significant level was set at 0.05/3 to account for multiple comparison. Once again, we evaluated the required minimum detectable effect size with 40 subjects per group to achieve 80% power. The results showed that the required minimum detectable effect size is $d=0.74$, which means the minimum detectable difference between placebo and bosentan group is 7.4. Although this is considered a large effect size ($d=0.8$, Cohen, 1988), we are confident in observing this difference based on previous studies.

Our power analysis is conservative because first the standard deviation of BP changes in placebo group should be much less than 10 mm Hg; Second, the power achieved in analysis of covariance (ANCOVA) is higher than that in ANOVA because the residual variance in ANCOVA is minimized.

[figure not shown]
FMD: In studies of VEGFR-TKI inhibitors, worsening in endothelial function is proportionate to the increase in blood pressure. Based on our previous work, we anticipate a $3\% \pm 4\%$ decrease in brachial artery FMD in subjects treated with placebo⁴⁴. Bosentan has previously been shown to improve endothelial function in hypertension⁷⁷, and we anticipate greater vascular function effects with ambrisentan. Like blood pressure outcome, we evaluated the required minimum detectable effect size with 40 subjects per group to achieve 80% power. Once again, as can be seen from Figure 8, the minimum detectable effect size (f) required is about 0.29. This is considered a medium effect size (f=0.25, Cohen, 1988) and we are confident in observing this effect size for FMD outcome based on previous studies.

Data Analysis Plan: We will use standard graphing and screening techniques to detect outliers and to ensure data accuracy. We will assess continuous outcomes for normality. If normality is violated, we will apply data transformation or consider non-parametric analysis methods. We will provide summary statistics for both numerical and categorical variables by study arms. We will assess comparability among randomization groups. Descriptive statistics for the study population, including means, medians, standard deviations, 25th percentile and 75th percentile for continuous variables as well as counts and percentages for dichotomous variables will be reported. Non-parametric Kruskal-Wallis tests will be conducted for continuous variables and Pearson Chi-square tests will be conducted for categorical variables to assess the comparability of demographic and clinical characteristics by study arms.

We will conduct analysis of covariance (ANCOVA), which answers the question whether the BP changes (or

Figure 8. Effect size vs. power

Effect Size	Power
0.1	0.15
0.13	0.22
0.16	0.32
0.19	0.44
0.22	0.56
0.25	0.68
0.28	0.78
0.31	0.86
0.34	0.92
0.37	0.96
0.4	0.98
0.43	0.99
0.46	1.0
0.48	1.0

the BP levels at the 4th week), partialling out BP levels at baseline, is different between study arms. Other covariates, such as age, gender, demographic characteristics will also be adjusted in the ANCOVA model. The regression coefficient of study arms and corresponding 95% confidence intervals (CI) will be presented and can be interpreted as the group difference on BP changes, after holding baseline BP and other covariates equal across groups. In addition to adjust linear relationship between the covariates and BP, we will employ a restricted cubic spline for continuous covariates to examine nonlinear relationship, which will provide more precise estimates for group effects. The number of knots was set at 3 because of the small sample size in the current study. We will also explore group by baseline BP levels interactions to examine whether the group effects vary by baseline BP levels. We expect minimal missing data due to the short follow-up for the study.

Bibliography/References

44. Mayer, E.L., *et al.* A Phase I dose-escalation study of the VEGFR inhibitor tivozanib hydrochloride with weekly paclitaxel in metastatic breast cancer. *Breast Cancer Res Treat* **140**, 331-339 (2013).

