2.0 Rationale and Specific Aim

We hypothesize that VEGFR-TKIs, ICIs, and combination treatment cause hypertension and vascular dysfunction through ET-1 induction and this pathway is a target for precision therapeutic interventions and novel risk stratification.

[figure not shown]
Aim

VEGFR-TKIs, ICIs, and the combination-mediated increases in ETA receptor activation will cause hypertension and reduce the bioavailability of endothelium-derived nitric oxide. We have previously demonstrated that two structurally distinct VEGFR TKIs reduce the bioavailability of endothelium-derived nitric oxide. We hypothesize that VEGFR TKIs antagonism will reduce digital microvessel hyperemia. As hypertension is mediated primarily in the microvasculature, we anticipate an enhanced response in this vascular bed.

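### The SAP's only multiplicity adjustment is a flat 0.05/3; if the final contrasts are tested at that level, Holm's step-down test would recover about 7 to 14 points of power at the same familywise error

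*SAP*

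**What the plan says.** The SAP's Sample Size and Power Calculation assumes that "the mean changes of BP for placebo group is 15 mm Hg", "the mean changes of BP for bosentan group is 7 mm Hg" and "the mean changes of BP for the ambrisentan group is 0 mm Hg", "all with a standard deviation of 10 mm Hg". It plans 45 per arm and computes power on 40. For the overall comparison it claims that "we will have 100% power to detect whether there is any significant differences among three study arms". For bosentan v placebo it states that "we will have 86.8% power to detect whether there is significant difference between two groups", and it explains the level used: "Significant level was set at 0.05/3 to account for multiple comparison". It does not list the three comparisons and gives no power for ambrisentan v bosentan.

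The SAP's Data Analysis Plan specifies an ANCOVA of blood pressure change (or the week 4 level) adjusted for baseline, and reports arm coefficients with 95% confidence intervals. It states no multiplicity rule for the tests.

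The protocol describes a different set of groups. Section 2.0 states: "We hypothesize that VEGFR-TKIs, ICIs, and combination treatment cause hypertension and vascular dysfunction through ET-1 induction". Section 5.0 plans 80 subjects on VEGF inhibitor, ICI, combination or none of these. Section 10.0 has neither a multiplicity level nor a list of contrasts.

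**The concern.** A flat 0.05/3 holds each contrast to the same strict threshold whatever the others show. Holm's rule compares the smallest of three p-values with 0.05/3, the next with 0.05/2 and the last with 0.05, stopping at the first that fails. It controls the familywise error at 5% under any dependence between the tests, and it rejects everything that Bonferroni rejects.

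The gain is greatest when some contrasts are almost certain to be rejected and others are not. The SAP assumes just that: one contrast of 15 mm Hg beside contrasts of 8 and 7 mm Hg. What is at stake is power on the smaller contrasts, including ambrisentan v bosentan, for which the SAP reports none.

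**Working it through.** **Inputs.** From the SAP: mean changes 15, 7 and 0 mm Hg; SD 10; n = 40 per arm; level 0.05/3 = 0.01667; cautious scenario 12 and 6. Assumed here: two-sided tests, three pairwise contrasts, no covariate gain, and ambrisentan kept at 0 in the cautious scenario, where the SAP does not restate it.

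**Step 1: reproduce the SAP's figure.** For bosentan v placebo, d = (15 − 7)/10 = 0.8. The noncentrality is d × √(n/2) = 0.8 × √20 = 3.578. On 78 degrees of freedom the two-sided critical value at 0.01667 is 2.447, and the noncentral t gives power of 86.8%, the stated figure. A one-sided test would give 91.9% and an unadjusted 0.05 would give 94.2%. So the two-sided 0.05/3 is what produced the SAP's number. The minimum detectable d at 80% power comes out at 0.737 (SAP: 0.74).

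**Step 2: bounds for each contrast.** Holm's power for a contrast cannot be below its power at 0.05/3 or above its power at 0.05 (t-test, 78 df):

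| Contrast | d | At 0.05/3 | At 0.05 |
|---|---|---|---|
| Ambrisentan v placebo | 1.5 | 100% | 100% |
| Bosentan v placebo | 0.8 | 86.8% | 94.2% |
| Ambrisentan v bosentan | 0.7 | 75.1% | 87.1% |
| Either 6 mm Hg contrast (12/6/0) | 0.6 | 59.5% | 75.5% |

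**Step 3: Bonferroni against Holm by simulation.** Error variance pooled over the three arms, 40 per arm:

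| Means | Contrast | 0.05/3 | Holm | Gain (points) |
|---|---|---|---|---|
| 15/7/0 | Bosentan v placebo | 87% | 94% | 7 |
| 15/7/0 | Ambrisentan v bosentan | 76% | 87% | 11–12 |
| 15/7/0 | All three rejected | 64% | 82% | 18 |
| 12/6/0 | Each 6 mm Hg contrast | 60% | 74% | 14 |
| 12/6/0 | All three rejected | 29% | 53% | 24 |

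Separate two-sample t-tests give nearly the same: 86.8% to 94.1%, 75.1% to 87.0%, and 59.6% to 73.2%. Under the global null the chance of any rejection is 4.4% for both procedures.

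**Step 4: the most that a single contrast can gain.** By the normal approximation the largest difference between power at 0.05 and at 0.05/3 is 2Φ((2.394 − 1.960)/2) − 1 = 2Φ(0.217) − 1 = 17.2 points (17.7 by the t-test with n = 40). At 40 per arm this needs d near 0.5, a difference of about 5 mm Hg, which is not among the SAP's assumptions.

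**The case against.** - **The final test level is not stated.** The 0.05/3 appears only in the power calculation. It is also Holm's first-step level, so powering at it would be a cautious choice for a Holm analysis. This stands: flat testing at 0.05/3 is the natural reading, not a written rule, and the gain is conditional on it. It does not remove the need to name a procedure.
- **Bonferroni is valid, and the contrast that the SAP powers reaches 86.8%.** This stands, and so the point concerns efficiency only.
- **Holm is not the only option.** For exactly three arms under the normal, equal-variance model, testing pairs at 0.05 after a significant overall F also controls the familywise error. It does at least as well (about 76% against 74% on the 6 mm Hg contrasts). This stands too, but it does not defend a flat 0.05/3.
- **The two documents describe different groups.** The SAP's arms do not appear in the protocol, so the contrasts cannot be fixed until that is settled. This stands and sets the order of work.

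A reader might infer a loss of about 17 points in this trial. Carrying the SAP's 0.05/3 to the protocol's 80 subjects, with 20 per group and effects of 15, 15 and 8 mm Hg against control, does take the 8 mm Hg contrast from 53% to 70%. But the equal split and the pattern of effects are not in the documents, so that figure is illustrative only. Nor do the documents make the ICI contrast the weakest. Protocol section 10.0 treats TKI, ICI and combination together and gives one mean change of 15 mm Hg. With 15 mm Hg in all three groups, power per contrast is 98.8% against 99.6%, a gain of under 1 point.

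**Conclusion.** The point holds as a cheap improvement. If the final contrasts are tested at a flat 0.05/3, Holm recovers about 7 points for bosentan v placebo and 11 to 12 for ambrisentan v bosentan on the SAP's main assumptions, and about 14 on each 6 mm Hg contrast in its cautious scenario, with no loss of error control. Under the main assumptions only ambrisentan v bosentan lies below 80% at 0.05/3, and Holm lifts it above 80% without added patients. The sizes rest on 40 evaluable per arm, SD 10, two-sided tests and three pairwise contrasts; ANCOVA would change the absolute powers. The size of the gain under the protocol's own groups cannot be fixed from the documents.

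**What to change.** 1. Reconcile the SAP's arms with the protocol's groups, then name the three group contrasts in the Data Analysis Plan.
2. State there that the three are tested by Holm's step-down rule (0.05/3, 0.05/2, 0.05) at a familywise 5%, in place of a flat 0.05/3.
3. State that the 95% intervals are descriptive and not adjusted for multiplicity.
4. In the power section, restate the pairwise power under Holm for all three contrasts, including the one now missing.

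The cost is a few SAP sentences and a short recalculation once the groups are settled; no patients or visits are added. The downside is that Holm has no simple matching simultaneous intervals, so a test and its interval can disagree. Little is lost by this, because the ordinary 95% intervals now planned do not match a 0.05/3 test either.

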5.0 Enrollment/Randomization

We will study 80 subjects with cancer who will be treated with VEGF inhibitor, ICI, or combination (VEGF inhibitor plus ICI or combination ICI treatment), or not receiving any of the above treatments and will serve as controls. We will restrict enrollment to age 40 - 75 years. Subjects will be identified by research staff from Vanderbilt Ingram Cancer Center (VICC) Clinics. If appropriate, the physician seeing the patient in clinic will approach the patient about participating in a clinical trial and alert the appropriate research staff for further study discussion with the patient. The patient will be consented or be allowed to take the consent form home to read if they are interested. We will use the VUMC Research Derivative, a fully identified clinical database specialized for research, to scan the population of patients in the VUMC electronic health record and use this information to approach patients with renal cell carcinoma, with the participants attending physicians' prior consent. Research coordinators at the Vanderbilt Translational and Clinical Cardiovascular Research Center (VTRACC) have had success in recruiting several thousand subjects in the last 5 years for a variety of projects. In addition to the VTRACC research staff, the study will also utilize services provided by the Vanderbilt Coordinating Center. The VCC will provide nursing support to assist the research coordinators with study procedures, consenting patients, placing the IV catheter, and collection of the endothelial samples.

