6.0 Study Procedures

Baseline. We will recruit subjects who have not yet begun their treatment. The subjects most recent labs will be reviewed by study staff as part of the screening process. Subjects will report to the Preston Research Building after a \geq 5 hour fast. First an informed consent will be obtained (if not already obtained during the patient's clinic visit), followed by a medical history, an abbreviated physical exam, and taking the subjects weight. After the patient has been sitting for 10 minutes, blood pressure will be measured in triplicate using an automated oscillometric device, baseline and hyperemic velocity time interval (VTI), and digital pulse amplitude tonometry will be performed to measure the reactive hyperemia index. We will draw blood for renal function, sodium and potassium, fasting glucose and insulin, metabolics, markers of inflammation, and markers of oxidative stress. We will measure urinary albumin/creatinine ratio (UACR). We will place an IV catheter for blood sampling and endothelial cell harvest. Endothelial cells (ECs) will be harvested from patients for gene expression (PCR, RNA-sequencing), staining and ATAC assays. Subjects will then have an ambulatory blood pressure monitor (Spacelabs) placed for 24 hours.

Follow-up Visit Approximately 1 month after starting treatment, subjects will return to the Preston Research Building. The procedures will be the same as the baseline visit procedures. We will start by discussing changes to medical history since the beginning of the study, conduct an abbreviated physical exam, and take the subjects weight. After the patient has been sitting for 10 minutes, blood pressure will be measured in triplicate using an automated oscillometric device, baseline and hyperemic velocity time interval (VTI), and digital pulse amplitude tonometry will be performed to measure the reactive hyperemia index. We will draw blood for renal function, sodium and potassium, fasting glucose and insulin, metabolics, markers of inflammation, and markers of oxidative stress. We will measure urinary albumin/creatinine ratio (UACR). We will place an IV catheter for blood sampling and endothelial cell harvest. Endothelial cells (ECs) will be harvested from patients for gene expression (PCR, RNA-sequencing), staining and ATAC assays. Subjects will then have an ambulatory blood pressure monitor (Spacelabs) placed for 24 hours.

Standard Techniques

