Peripheral Artery Tonometry Digital pulse amplitude will be measured in the fasting state with a peripheral artery tonometry (PAT) device placed on the tip of each index finger (Endo-PAT2000, Itamar Medical, Caesarea, Israel). The PAT device comprises a pneumatic plethysmograph that applies uniform pressure to the surface of the distal finger, allowing measurement of pulse volume changes in the finger. Throughout the study, the inflation pressure of the digital device is electronically set to 10 mm Hg below diastolic blood pressure or 70 mm Hg (whichever is lower). Baseline pulse amplitude is measured from each fingertip for 2 minutes 20 seconds. Arterial flow is arrested for 5 minutes by a cuff placed on a proximal forearm (Hokanson AG101, D.E. Hokanson Inc, Bellevue, WA) at whichever occlusion pressure would be higher: 200 mm Hg or 60 mm Hg plus systolic blood pressure. Pulse amplitude is recorded electronically in both fingers and analyzed by a computerized, automated algorithm (Itamar Medical) that provides the average pulse amplitude for each 30-second interval after forearm cuff deflation up to 4 minutes. To determine the PAT ratio, we will first calculate the ratio of the post-deflation pulse amplitude to the baseline pulse amplitude in the 90- to 120-second postdeflation time period (ie, $X_{h90-120}/X_{h0}$: with h denoting hyperemic finger and 0 denoting baseline, X being the pulse amplitude). Then, we divided this result by the corresponding ratio from the contralateral, control hand (ie, $X_{c90-120}/X_{c0}$: with c denoting the control finger and 0 denoting baseline) to obtain the PAT ratio. Because PAT ratio has a heteroscedastic error structure, we use natural logarithm transformation in all analyses such that PAT ratio= $\ln[(X_{h90-120}/X_{h0})/(X_{c90-120}/X_{c0})]$.

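### The SAP powers brachial FMD, which the protocol never measures, while the digital hyperemia outcome behind the vascular hypothesis has no model, contrast or detectable difference

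*SAP*

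**What the plan says.** **SAP, Sample Size and Power Calculation.** After blood pressure, the SAP treats one further outcome, FMD. It anticipates a 3% ± 4% "decrease in brachial artery FMD in subjects treated with placebo" and gives no mean for the bosentan or ambrisentan arm. With 40 per group and 80% power, it says that "the minimum detectable effect size (f) required is about 0.29. This is considered a medium effect size", and that "we are confident in observing this effect size for FMD outcome based on previous studies".

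**SAP, Data Analysis Plan.** The ANCOVA takes BP change or week-4 BP as outcome and baseline BP as covariate. Its arm coefficient "can be interpreted as the group difference on BP changes, after holding baseline BP and other covariates equal across groups". PAT and VTI are not named anywhere in the SAP.

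**Protocol, 2.0.** The vascular hypothesis reads: "We hypothesize that VEGFR TKIs antagonism will reduce digital microvessel hyperemia".

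**Protocol, 5.0.** "We will study 80 subjects with cancer who will be treated with VEGF inhibitor, ICI, or combination", with untreated patients as controls. No group sizes are given.

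**Protocol, 6.0.** Both visits include baseline and hyperemic VTI, and "digital pulse amplitude tonometry will be performed to measure the reactive hyperemia index". The Peripheral Artery Tonometry subsection fixes the formula, the 90 to 120 second window and the scale: "Because PAT ratio has a heteroscedastic error structure, we use natural logarithm transformation in all analyses". FMD and arterial diameter appear nowhere in the protocol.

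**Protocol, 10.0.** Power is discussed for blood pressure only.

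**The concern.** The SAP and the protocol name different vascular outcomes. An analyst following the SAP would look for an FMD variable that no visit produces. For PAT, which is collected and which the hypothesis is about, the analyst would find a formula and a log scale but no model, comparison or alpha.

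Several choices could then be made after the data are seen: follow-up value or change, each treatment against control or all treated pooled, between-group or within-subject, PAT or VTI. A reader of the SAP would also take from it an assurance of 80% power at f = 0.29 that belongs to another outcome, other arms and 120 analysed patients.

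**Working it through.** **1. Reproduce the SAP's figure.** Inputs from the SAP: k = 3 arms, n = 40 each, N = 120, 80% power. The alpha for the overall test is not stated; 0.05 is assumed.

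Power = P[F′(k−1, N−k, λ) > F crit], where F′ is noncentral F and λ = f²N.

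- At f = 0.29, λ = 0.0841 × 120 = 10.09 and power is 80.9%.
- Power is exactly 80% at f = 0.287.

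The stated value of about 0.29 is correct for that design, and the points tabulated from Figure 8 between f = 0.10 and 0.43 also reproduce.

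**2. Compare the outcomes.**

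| Item | SAP | Protocol |
|---|---|---|
| Vascular outcome | Brachial FMD | Digital PAT, hyperemic VTI |
| Groups | Placebo, bosentan, ambrisentan | VEGF inhibitor, ICI, combination, untreated |
| Number | 3 × 45 recruited, 3 × 40 analysed | 80 in total, no split |
| Model for the vascular outcome | None written; ANCOVA is for BP | None; PAT formula and log scale only |

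**3. Same formula for 80 subjects.** Equal groups are an assumption, because the protocol gives no split. The SAP's own loss allowance gives 80 × 40/45 = 71.1, rounded here to 72 so that it divides evenly.

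| Groups | Minimum f, no loss | Power at f = 0.29 | Minimum f, about 72 analysed | Power at f = 0.29 |
|---|---|---|---|---|
| 2 | 0.317 (2×40) | 73% | 0.335 (2×36) | 68% |
| 3 | 0.359 (3×26) | 61% | 0.374 (3×24) | 57% |
| 4 | 0.379 (4×20) | 55% | 0.401 (4×18) | 50% |

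**4. Pairwise detectable differences.** Two-sided noncentral t, 80% power, no loss, unadjusted. The noncentrality is d√(n/2) for n per group.

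- Alpha 0.05: d = 0.63 (40 v 40), 0.79 (26 v 26), 0.91 (20 v 20).
- Each treatment against control with alpha split: d = 0.88 (three groups, 0.05/2, 26 v 26) and 1.06 (four groups, 0.05/3, 20 v 20).

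The documents give no SD for the ln PAT ratio, so these stay in SD units.

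**5. Effect of baseline adjustment.** ANCOVA multiplies the detectable difference by √(1 − r²), in follow-up SD units, where r is the baseline to follow-up correlation. The documents give no r. For r = 0.3, 0.5 and 0.7 the factor is 0.95, 0.87 and 0.71, so 1.06 SD would become 1.01, 0.92 or 0.76. This supposes balanced baselines. The groups are defined by therapy received, so imbalance could take back part of the gain.

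**The case against.** The strongest counter-argument is that this is one symptom of a SAP written for another design. Every power statement in it assumes placebo, bosentan and ambrisentan arms, and replacing the FMD paragraph alone would leave the BP text unreconciled. That stands as context, and the wider mismatch needs its own correction. The vascular gap would remain even then, because correcting the arms would not give PAT a model.

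Second, no outcome is ranked as primary, both documents lead with hypertension, and PAT is not wholly open: the protocol fixes its window, control-finger correction and log scale, and the SAP has general text on checking and transforming continuous outcomes. This narrows the gap without closing it. Neither document extends the BP ANCOVA to other outcomes, and the SAP's arms could not supply a contrast among the protocol's groups.

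Third, a before-and-after test within subjects is a natural reading of the hypothesis, and between-group figures do not cover it. That is fair. Paired, at 80% power and two-sided 0.05, the detectable change is 0.66 SD of the change with 20 subjects and 0.45 with 40. Those SD units differ from the ones above, so the figures are not directly comparable. That both tests are plausible is a reason to name one in advance.

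Fourth, applying the 45-to-40 loss to 26 per group gives 23.1, not 24. With 3 × 23 the minimum f is 0.38 and power at 0.29 is 55%, which does not change the conclusion.

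**Conclusion.** The concern holds and must be fixed. The SAP powers an outcome that the protocol does not collect, and the outcome that carries the vascular hypothesis has no prespecified test. Both statements come directly from the text and need no assumption.

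The size of the power shortfall does rest on assumptions: equal groups, overall alpha 0.05, and either no loss or the SAP's own loss rate. Across two to four groups the minimum detectable f runs from 0.32 to 0.40, and power at 0.29 from 73% down to 50%. The SAP's arithmetic is sound but belongs to a different study.

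A smaller point is naming. The visit paragraphs call the PAT result a reactive hyperemia index without defining it, while the PAT subsection defines only the ln PAT ratio. The documents do not show whether the two differ numerically.

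**What to change.** 1. Delete the FMD paragraph from the SAP's power section.
2. Name the ln PAT ratio, as defined in protocol 6.0, as the digital hyperemia outcome, and use that name in both visit paragraphs. If the index is a separate measure, define it there.
3. Add to the SAP: *Follow-up ln PAT ratio will be analysed by ANCOVA on the protocol's treatment groups (VEGF inhibitor, ICI, combination, untreated control), adjusted for baseline ln PAT ratio and the covariates listed for BP.* If a within-subject change is the intended test of the hypothesis, say so and specify it instead. Because the groups are not randomised, say how confounding by group is handled.
4. State the contrasts, for example each treatment group against untreated controls, and match alpha to their number.
5. Declare planned group sizes within the 80, then give the minimum detectable difference after expected dropout, saying which SD it is expressed in.
6. State the role of VTI.

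The cost is wording in the SAP and protocol, with no new measurement. The stated detectable effect will look less favourable than 0.29, and the sponsor must commit to group sizes.

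### The SAP is written for a three-arm placebo/bosentan/ambrisentan trial, not for the protocol's 80 patients grouped by cancer treatment, and the protocol's 100% power for 8 mm Hg fails as a between-group claim

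*SAP*

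**What the plan says.** **SAP, Sample Size and Power Calculation.** The design has three arms: placebo, bosentan and ambrisentan. The expected BP changes are 15 mm Hg on placebo, 0 on ambrisentan, and for the middle arm "the mean changes of BP for bosentan group is 7 mm Hg", all with SD 10. On numbers, "We planned to recruit 45 patients per group", with 40 per group used for power. For pairwise tests, "Significant level was set at 0.05/3 to account for multiple comparison". The key pairwise result is "When comparing bosentan group to the placebo, with 40 subjects per group, we will have 86.8% power to detect" a difference, and "the minimum detectable difference between placebo and bosentan group is 7.4" (mm Hg) at 80% power. A second outcome is powered from an anticipated fall in "brachial artery FMD in subjects treated with placebo".

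**SAP, Data Analysis Plan.** "We will assess comparability among randomization groups". The main model is an ANCOVA asking whether BP change, or week-4 BP, "partialling out BP levels at baseline, is different between study arms". Only BP is named, without a device or component.

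**Protocol, sections 2.0, 4.0, 5.0 and 6.0.** There are 80 subjects in all: patients treated with a VEGF inhibitor, an ICI or a combination, and controls receiving none of these. Section 5.0 has Randomization in its heading but describes no allocation. Visits are at baseline and about one month after treatment starts. The vascular measures are digital pulse amplitude tonometry (analysed as a log PAT ratio) and hyperemic VTI. The Aim in section 2.0 concerns digital microvessel hyperemia. BP is taken by aneroid, oscillometric and 24-hour ambulatory methods.

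**Protocol, section 10.0.** It assumes a mean BP change of 15 mm Hg with SD 10, refers to an ANOVA framework, and claims 100% power for a difference of 8 mm Hg. It gives no group sizes, alpha or contrast.

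**The concern.** Placebo, bosentan and ambrisentan appear nowhere in the protocol, and FMD is not among its procedures. The SAP therefore fixes neither the comparisons this study will make nor their alpha level, and it has no plan for the tonometry outcome that the Aim concerns. The BP measure is also open, with three methods available. Unless these are settled before analysis, they will be chosen with the data in hand, in a non-randomized comparison where such choices already carry more weight.

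The protocol's power sentence appears to descend from the SAP: it has the same 15 mm Hg and SD 10, and its 8 mm Hg equals the SAP's placebo-bosentan gap (15 − 7). Yet for that same gap and SD the SAP reports 86.8%, with 40 per group at 0.05/3. A claim of 100% from 80 subjects spread over up to four groups needs checking. If sensitivity is overstated, a null result could be read as absence of effect. The risk is greatest for ICI alone, for which the documents give no BP figure.

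**Working it through.** **Inputs.** From the protocol: N = 80, SD 10 mm Hg, difference 8 mm Hg, mean change 15 mm Hg. From the SAP: 45 and 40 per group, means 15/7/0, pairwise alpha 0.05/3. Assumed, because section 10.0 is silent: a two-sided test at 0.05 (0.05/3 also shown) and the group splits.

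**Formula.** For two groups, noncentrality δ = Δ / (SD × √(1/n₁ + 1/n₂)). Power is the probability that a noncentral t with n₁ + n₂ − 2 df exceeds the two-sided critical value. No gain from covariates is included unless stated.

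**1. The SAP's own figures reproduce.** Means 15, 7 and 0 have grand mean 7.33, and f = √[(7.67² + 0.33² + 7.33²)/3] / 10 = 0.613 (stated 0.61). Omnibus power with 40 per group is above 99.99% (stated 100%). For bosentan vs placebo, δ = 8 / (10 × √(2/40)) = 3.578 against a critical value of 2.447, giving 86.8% (stated 86.8%). The minimum detectable difference is 7.37 (stated 7.4). The SAP's arithmetic is correct for its design, so the problem is that the design is not this one: 3 × 45 = 135 planned subjects against 80.

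**2. Ceiling for the protocol's 8 mm Hg.** If group means lie within a range of 8, the between-group noncentrality is at most 80 × (8/2)² / 10² = 12.8, whatever the split. At 0.05 that gives at most:
- 94.2% for two groups or any single contrast
- 89.1% for a three-group F test
- 84.5% for a four-group F test

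**3. Specific splits, SD 10.**

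| Comparison | Alpha | 8 mm Hg | 12 mm Hg | 15 mm Hg | Min. detectable (80%) |
|---|---|---|---|---|---|
| 40 vs 40 | 0.05 | 94.2% | – | – | – |
| 20 controls vs 60 treated | 0.05 | 86.4% | – | – | – |
| 20 vs 20 | 0.05 | 69.3% | 95.9% | 99.6% | 9.1 |
| 20 vs 20 | 0.05/3 | 51.6% | 89.5% | 98.5% | 10.6 |
| 18 vs 18 | 0.05/3 | 46.2% | 85.4% | 97.2% | 11.3 |
| 10 treated vs 20 controls | 0.05/3 | 33.2% | 70.7% | 89.9% | 13.2 |

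The 18 applies the SAP's attrition: 20 × 40/45 = 17.8. Using the pooled error from four groups of 20 (76 df) changes the 20 vs 20 row at 0.05/3 only slightly: 53.5%, 90.8%, 98.8% and 10.4 mm Hg.

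**4. Readings that do reach about 100%.** A before-after t-test (δ = 8/10 × √n, n − 1 df, 0.05) gives 92.4% for n = 20, 99.9% for n = 40 and over 99.99% for n = 60. Pooling over groups therefore gets there, but that test does not use the controls, and one group of 20 falls short. Between groups, reaching 99.5% (which rounds to 100%) needs an SD of at most 7.8 for 40 vs 40 or 5.4 for 20 vs 20.

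**The case against.** **ANCOVA lowers the residual SD, so 94.2% is not a true ceiling.** This stands as a qualification. The ceiling is for an unadjusted test with SD exactly 10, two-sided at 0.05. If change correlates with baseline at r, the residual SD is 10 × √(1 − r²). Assumed values of r = 0.3, 0.5 and 0.6 raise 40 vs 40 to 95.9%, 98.3% and 99.3%. A one-sided 0.05 test gives about 97%. The documents supply no such correlation, no one-sided test and no two-group split of 40. Section 10.0 says the SD should be well below 10, but it states its power under SD 10.

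**Section 10.0 may mean a within-subject change.** It gives one mean change and no second group mean, and a pooled before-after reading does reproduce. But it cites ANOVA and section 5.0 enrols controls, so a between-group reading is the natural one. Either way, the sentence cannot be verified without its contrast, alpha and group sizes.

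**The core analysis survives.** This is true: the baseline-adjusted ANCOVA with arm coefficients and 95% intervals can be run on the protocol's groups, with controls as the natural reference. At 15 mm Hg, the only BP effect the protocol assumes, groups of 20 are well powered if controls do not change. That limits the damage but does not supply the missing contrasts, alpha or BP measure.

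**The replacement figures borrow 0.05/3 and attrition from the SAP.** The 0.05/3 has its own justification here, since three treated groups against control make three contrasts. The 18 per group and all the splits are illustrations, and the SAP itself expects little missing data.

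**Conclusion.** The concern holds. The SAP's arms, pairwise contrasts, sample size, power and FMD text belong to a different trial, and only its generic ANCOVA carries over. The protocol's 100% power for 8 mm Hg does not reproduce as a between-group claim: at SD 10, two-sided 0.05, unadjusted, it is at most 94.2% for any split of 80 and 69.3% for 20 vs 20. At 0.05/3 the minimum detectable difference is 10.6 mm Hg with 20 per group, or 11.3 with 18, against the 7.4 in the SAP. The 94.2% bound does not depend on the split. The per-group figures assume four equal groups, which the protocol does not state, and an unequal split would be worse for the smaller groups. The shortfall matters for effects near 8 mm Hg and much less at 15. This must be fixed, because the plan does not currently prespecify this study's comparisons.

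**What to change.** 1. **Reconcile the SAP with the protocol's groups.** Remove the placebo, bosentan, ambrisentan, randomization and 45/40-per-group text. Before analysis, name one BP measure (for example mean arterial pressure from one stated device, since the 15 mm Hg figure is mean arterial pressure). Name the contrasts and their alpha (for example each treated group vs control at two-sided 0.05/3).
2. **Settle the control group.** Section 4.0 admits patients on no treatment at all, while section 5.0 defines controls as receiving none of the listed treatments. These must be reconciled. The follow-up visit is dated from starting treatment, so its timing for controls must also be stated.
3. **Replace the power text in the SAP and section 10.0** with figures for N = 80 and the expected split. With 20 per group, for example: at SD 10 and two-sided 0.05/3, the minimum detectable pairwise difference at 80% power is 10.6 mm Hg (11.3 with 18 completers per group), and power is 51.6%, 89.5% and 98.5% for 8, 12 and 15 mm Hg. Any gain claimed from ANCOVA should come with the correlation assumed.
4. **Replace FMD with a vascular outcome the protocol measures.** The log PAT ratio fits the Aim most directly. The documents give no SD for it, so state its minimum detectable difference in SD units (1.06 SD at 20 per group, 1.13 at 18, at 0.05/3) until one is available.

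Optionally, because groups follow treatment received, adjust for the number of antihypertensives at entry.

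The cost is an SAP rewrite, a corrected section 10.0 and a less favourable stated power. No new data are needed.
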